1 AMENDMENTS FROM PREVIOUS VERSION(S)

Included the initiation of 2nd line of therapy as a censoring event in the definition of progression-free survival. This was inadvertently omitted from the SAP and was identified after an author review of the definition provided in the manuscript draft.

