2.2 Study Objectives

Primary Objectives:

- 1) *Among patients with HR+/HER2- A/MBC receiving palbociclib combination therapy with AI as first-line therapy:*
 - a. *Describe demographic and clinical characteristics.*
 - *Demographic characteristics will include age, sex, race, insurance status, menopausal status, and region of residence at A/MBC diagnosis.*

[figure not shown]
PFIZER CONFIDENTIAL

- *Clinical characteristics will include variables such as, stage of initial diagnosis, histology, Eastern Cooperative Oncology Group (ECOG) performance status (where ECOG score unavailable, Karnofsky performance status will be converted to corresponding ECOG score) and comorbid disease burden utilizing the Charlson Comorbidity Index, HER2 and estrogen receptor (ER)/ progesterone receptor (PR) status, BRCA status, number and sites of distant metastasis at A/MBC diagnosis (visceral (defined as liver, lung, peritoneum, and pleural nodules), non-visceral, bone only); modalities of treatment received prior to A/MBC diagnosis (chemotherapy, hormone therapy, surgery, radiation therapy) documentation of endocrine sensitivity and endocrine resistance if hormone therapy was received in the adjuvant setting, time to metastasis (time between initial and metastatic diagnosis) and disease free interval (time between completion of adjuvant therapy and diagnosis of A/MBC).*
- b. *Describe treatment patterns.*
 - *Distribution of regimens from the diagnosis of A/MBC through the end of the record.*
 - *Sequence of regimens across lines, through the end of the record of systemic therapy.*
 - *Description of the dosing will include the starting dose, end dose, dose adjustment (dose increase and dose reduction), type of dose adjustment (dose modification, schedule changes, dose delay, or hold) discontinuation, reason (including progression, end of planned therapy, insurance changes, schedule change, dose delay, hold, cost, patient refusal, toxicity), and time to dose adjustment (discontinuation).*
- 2) *Among patients receiving palbociclib + AI as first-line therapy, examine clinical effectiveness outcomes including:*
 - a. *Real-world progression-free survival (rwPFS) will be assessed for the first-line therapy.*
 - b. *Real-world overall survival (rwOS) will be assessed from the start of the first-line therapy.*
 - c. *Real-world time to next therapy (rwTTNT) will be assessed from the start of the first-line therapy.*

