5 ENDPOINTS AND COVARIATES

Primary Endpoints-

1. To summarize the demographic and clinical characteristics.
Demographic characteristics will include

PFIZER CONFIDENTIAL

- Year of initial, metastatic and AMBC diagnoses;
- age at initial diagnosis, A/MBC diagnosis, start of palbociclib treatment and death;
- sex;
- race;
- ethnicity
- insurance status;
- menopausal status;
- region of residence at A/MBC diagnosis.

Clinical characteristics will include

[figure not shown]
- stage of initial diagnosis;
- histology;
- Eastern Cooperative Oncology Group (ECOG) performance status (where ECOG score unavailable, Karnofsky performance status will be converted to corresponding ECOG score);
- prior surgery (and type);
- prior radiation therapy (and type);
- comorbid disease burden (see Section 9.2);
- Charlson comorbidity index
- Sites of metastasis – visceral (liver, lung, peritoneum and pleural nodules), non-visceral, bone only
- Number of metastatic sites
 - Number of lesions in the site
 - Disease burden in the liver, lungs, bone
- time to metastasis (time between initial and metastatic diagnoses)
- HER2 and estrogen receptor (ER)/ progesterone receptor (PR) status;
- BRCA status
- modalities of treatment received prior to A/MBC diagnosis (chemotherapy, hormone therapy, surgery, radiation therapy);
 - Documentation of endocrine sensitivity and endocrine resistance if hormone therapy received in adjuvant setting
- disease free interval (time between completion of adjuvant therapy and diagnosis of A/MBC).

2. To summarize treatment patterns.

Treatment patterns will be evaluated by the review of

- the distribution of regimens;
- sequence of regimens across the lines;
- description of dosing which will include the starting dose, end dose, dose adjustment (dose increase and dose reduction), type of dose adjustment (dose modification, schedule changes, dose delay or hold), discontinuation reason (including death, progression, end of planned therapy, insurance changes, schedule change, dose delay, hold, cost, patient refusal, toxicity), and time to dose adjustment

PFIZER CONFIDENTIAL

[figure not shown]

3. To summarize the effectiveness outcomes of treatment-
 - a. Real-world progression-free survival (rwPFS) for the first-line therapy at time points 3, 6, 12, 18, 24, 30, and 36 months;
 - b. Real-world overall survival (rwOS) from the start of the first-line therapy at time points 6, 12, 18, 24, 30, and 36 months.

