of the 2nd line for patients with >1 line of therapy, date of last contact, or end of study period.

- Real world time to treatment discontinuation (rwTTD)- It is defined as length of time from the start of palbociclib + AI treatment to the earliest of the following: date the patient discontinues first-line treatment, date of death, last known usage of first-line treatment, or end of study period.
- Real world time to next treatment (rwTTNT)- It is defined as length of time from the start of palbociclib + AI treatment to the earliest of the following: subsequent line of therapy initiation, date of death, date of last contact, or end of the study period.
- Real world time to chemotherapy (rwTTC)- It is defined as length of time from the start of palbociclib + AI treatment to the earliest of the following: the day before the start of subsequent chemotherapy for patients with evidence of chemotherapy, or date of death for any reason. Or, where censored, the latest of date of last contact, or end of the study period.
- Real world time to dose adjustment (rwTTDA)- It is defined as length of time from the start of palbociclib + AI treatment to the earliest of the following: date of first-line treatment dose adjustment, date of death, date of first-line treatment discontinuation, date of last contact or end of study period.

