Kaplan-Meier survival analysis is used to descriptively characterize time to event outcomes. In this study, following time to event outcomes will be analyzed-

- Time to Real-world overall survival (rwOS)

[figure not shown]
The time origin for analysis of rwOS is start of the first-line therapy, and the terminal event is death. For patients not known to be deceased at the time of analysis, rwOS will be censored at the earliest of the last date of last contact or the end of the study period.

- Time to Real-world progression-free survival (rwPFS)

The time origin for analysis of rwPFS is start of the first-line therapy. Patients without a clinician-assessed progression event or death will be censored at the earliest of the following events: date of initiation of the 2nd line for patients with >1 line of therapy, date of last contact, or end of study period.

- Real world time to treatment discontinuation (rwTTD)

PFIZER CONFIDENTIAL

The time origin for analysis of rwTTD is start of the first-line therapy. Patients without first-line treatment discontinuation and who did not die will be censored at the earliest of the following events: last known usage of first-line treatment, or end of study period.

- Real world time to next treatment (rwTTNT)

The time origin for analysis of rwTTNT is start of the first-line therapy. Patients without a subsequent line of therapy initiation and who did not die will be censored at the earliest of the following events: date of last contact, or end of the study period.

- Real world time to chemotherapy (rwTTC)

The time origin for analysis of rwTTC is start of the first-line therapy. Patients who did not receive subsequent chemotherapy and who did not die will be censored at the latest of the following events: date of last contact, or end of the study period.

- Real world time to dose adjustment (rwTTDA)

The time origin for analysis of rwTTDA is start of the first-line therapy. Patients without a first-line treatment dose adjustment will be censored at the earliest of the following events: first-line treatment discontinuation, date of death, date of last contact, or end of the study period.

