One Kaplan-Meier analysis is generated for each time to event endpoint. Kaplan-Meier analysis will include number of patients with events and censored patients, median, 25th percentile and 75th percentile times to event (in months), 95% CI of the quartiles and ranges (minimum and maximum). Kaplan-Meier analysis will be repeated in the subgroup of patients who received a starting dose of 125mg.

One Cox regression analysis will be generated for each time to event endpoint, provided the sample size supports the analysis. Demographic and baseline clinical characteristics, some examples are detailed in section 7.1, will be included to the extent that sample size permits. Results from this analysis results will include parameter estimates, p-values, standard errors, hazard ratios and 95 % CIs of hazard ratios. The proportional hazards assumption will be assessed graphically with the inspection of Schoenfeld residuals and by including interaction terms between the variables and log(time).

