Therapy start date	Year, month, day
Therapy end date	Year, month, day
Start reason	Recurrence; Progression; Other reason not related to worsening disease
Start reason source date	Year, month, day (can be linked to clinician confirmation date of recurrence/progression if start reason is recurrence/progression)
Stop reason	Categories including: Progression; Toxicity; End of planned therapy; Insurance changes; Treatment ongoing; Other
Stop reason source date	Year, month, day (can be linked to clinician confirmation date of recurrence/progression if stop reason is recurrence/progression)
Treatment part of clinical trial	Yes; No
Palbociclib-specific variables (captured in addition to above variables)	
Combination AI partner	Letrozole, Anastrozole, Exemestane
Concomitant LHRH Agonists	Goserelin (Zoladex), Histrelin (Vantas), Leuprolide (Eligard, Lupron), Triptorelin (Trelstar)
Dose 1 (start dose)	125mg, 100mg, 75mg
Dose 1 start date	Year, month, day
Dose n (where n>=2)	125mg, 100mg, 75mg
Dose n start date	Year, month, day
Dose n adjustment type or reason	Categories include schedule change; dose delay; hold; cost; patient refusal; toxicity

Variables that will be derived from curated data will include the following:

Data Elements	Description
-----------------------------	---------------------------

PFIZER CONFIDENTIAL

Age at A/MBC diagnosis	Age in years; age categories: <50, 50-64, 65 –74, ≥75 years (Exact list will depend on the expert de-ID approach)
Age at start of palbociclib treatment	Age in years; age categories: <50, 50-64, 65 –74, ≥75 years
Date of death	If patient vital status = deceased, date of death from the medical record (capturing from EMR, registries, third party integrations) (Availability of the exact date will depend on the Expert de-ID approach)
Palbo dose change ever	Yes; No
Disease Free Interval (DFI)	Months from the end of adjuvant therapy to the date of disease recurrence ≤12 months, 13-24 months, 25-36 months >36 months Unknown
Endocrine sensitivity	≥12 months without recurrence/progression after completion of endocrine therapy in the adjuvant setting

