Real-world progression free survival (rwPFS)	Length of time from the start of palbociclib + AI treatment to the earliest of the following: clinician-assessed progression event, date of death, date of last contact, or end of study period. Progression identified from tissue/pathology or imaging/radiology and confirmed by clinician (in 2 separate data points), from MA guidance: 
1. Medical Oncology Consult/Note (can also include medical oncologist history and physical (H&P))2. Radiation Oncology note/consult/(can also include radiation oncology H&P)3. Progress Note (can also include /H&P/Consult - use this option for physician of other discipline in the absence of numbers 1 and 2)4. Discharge Summary5. Nursing Note6. Care Everywhere/Scanned Documents/External lab reports (for information diagnosed outside of facility for which patient is being abstracted)7. Other
Real world time to treatment discontinuation (rwTTD)	Length of time from the start of palbociclib + AI treatment to the earliest of the following: date the patient discontinues first-line treatment, date of death, last known usage of first-line treatment, or end of study period
Real world time to next treatment (rwTTNT)	Length of time from the start of palbociclib + AI treatment to the earliest of the following: subsequent line of therapy initiation, date of death, date of last contact, or end of the study period

Real world time to dose adjustment (rwTTDA)	Length of time from the start of palbociclib + AI treatment to the earliest of the following: date of first-line treatment dose adjustment, date of death, last known usage of first-line treatment, or end of study period.
Real world time to chemotherapy (rwTTC)	Length of time from the start of palbociclib + AI treatment to the earliest of the following: the day before the start of subsequent chemotherapy for patients with evidence of chemotherapy, or date of death for any reason. Or, where censored, the latest of date of last contact, or end of the study period.

PFIZER CONFIDENTIAL

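### The SAP gives conflicting rules for rwPFS at second-line start: Section 5.1 stops the clock there, Appendix 2 ignores it, and Section 7.2 does not confine events to those on or before it

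*SAP*

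**What the plan says.** Three current texts in the SAP define rwPFS.

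- **Section 5.1** runs time from the start of palbociclib + AI to the earliest of progression, death, or initiation "of the 2nd line for patients with >1 line of therapy, date of last contact, or end of study period". It does not label any of these dates as event or censoring. Section 1 supplies the label: "Included the initiation of 2nd line of therapy as a censoring event in the definition of progression-free survival".
- **Section 7.2, Objective 2** gives the analysis rule: "Patients without a clinician-assessed progression event or death will be censored at the earliest of the following events: date of initiation" of the second line (2L), last contact or study end.
- **Appendix 2 (Section 9.2)** gives the endpoints as "clinician-assessed progression event, date of death, date of last contact, or end of study period", with no 2L term. The row stands in the list headed "Variables that will be derived from curated data will include the following".

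The scope of the endpoint is stated in Section 2.2, "Real-world progression-free survival (rwPFS) will be assessed for the first-line therapy", and again in Section 5, "Real-world progression-free survival (rwPFS) for the first-line therapy at time points". For the analysis itself, Section 7.2 says "One Kaplan-Meier analysis is generated for each time to event endpoint". It repeats this only by subgroup. No section says which definition governs.

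**The concern.** A patient who starts 2L therapy without a recorded progression is handled differently depending on which section is programmed. Both the time and the event status can change. The rwPFS median, quartiles, landmark estimates and Cox model all use them.

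Section 7.2 has a further fault if taken at its word. It censors at 2L start only patients who never progress or die, so whether someone is censored at the switch depends on what happens afterwards. Kaplan-Meier censoring may not depend on the future in that way.

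A secondary point is that censoring at 2L start is valid only if switching is unrelated to progression risk, and the plan has no analysis that examines this. rwTTNT, rwTTD and the discontinuation reasons give context but do not test it.

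**Working it through.** The SAP has no planned rwPFS median, event count or power that depends on this rule, so there is no figure of its own to reproduce. The check is to apply each text to the same patients.

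**1. Two patients, no assumptions**

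Patient A starts 2L at month 10 with no recorded progression and dies at month 18. Patient B starts 2L at month 10, has no later event, and has last contact at month 30.

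| Reading | Patient A | Patient B |
|---|---|---|
| Section 5.1 with Section 1 | censored at 10 | censored at 10 |
| Section 7.2, literal | event at 18 | censored at 10 |
| Appendix 2 | event at 18 | censored at 30 |
| Time from 5.1, status from literal 7.2 | event at 10 | censored at 10 |

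A and B are alike at month 10. Literal Section 7.2 keeps A at risk because A later dies, and removes B because B does not. The last row shows that taking the time from one section and the status from the other creates a fourth answer: a death dated eight months early.

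**2. Illustration of size**

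From the SAP: starts 03 February 2015 to 31 July 2019, assumed cutoff 01 February 2020 (about 6 to 60 months of follow-up), and 300 to 400 patients.

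Assumed:
- exponential progression with true median 24 months, so λ = ln 2 / 24 = 0.0289 per month;
- 10% per year lost to follow-up;
- 2L starts without documented progression at a rate q = 0.1, 0.2 or 0.3 of the true progression rate;
- a share f of these starts are unrecorded failures, with 2L one month after failure and the next documented event a median of 12 months later;
- the other switches multiply the later hazard by h.

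*No switch is a failure (f = 0).* Censoring at the switch is then independent, so the Section 5.1 median stays at 24. Under Appendix 2,

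S(t) = e^(-(1+q)λt) + [q/(1+q-h)] × [e^(-hλt) - e^(-(1+q)λt)].

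For q = 0.2 and h = 2 this is 1.25e^(-1.2λt) - 0.25e^(-2λt), which equals 0.5 at t = 22.8. The difference is 24.0 - 22.8 = +1.2 months.

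*Every switch is an unrecorded failure (f = 1).* The documented hazard is about (1-q)λ, so the Section 5.1 median is about 24/(1-q), or 24/0.8 = 30.0 at q = 0.2. Simulation of 400,000 patients gives 30.2, against 27.8 under Appendix 2.

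Simulated Section 5.1 median minus Appendix 2 median, in months:

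| Case | q = 0.1 | q = 0.2 | q = 0.3 |
|---|---|---|---|
| f = 1 | +0.9 | +2.4 | +4.6 |
| f = 0.5, h = 1 | +0.4 | +0.9 | +1.7 |
| f = 0, h = 0.5 | -0.5 | -1.0 | -1.4 |
| f = 0, h = 1 | about 0 | about 0 | about 0 |
| f = 0, h = 2 | +0.7 | +1.2 | +1.8 |
| f = 0, h = 4 | +1.3 | +2.4 | +3.3 |

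These carry simulation error of about 0.1 to 0.2 months. At q = 0.2, literal Section 7.2 gave a shorter median than Section 5.1 in every case (for example 23.1 against 24.1 at f = 0, h = 1).

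Across these cases, of 300 to 400 patients, 14-20, 28-39 and 40-59 (q = 0.1, 0.2, 0.3) are censored at 2L start under Section 5.1. Of those, 4-15, 7-29 and 10-42 become events under Appendix 2.

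**3. Sensitivity**

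At q = 0.2 and f = 1, a true median of 18 gives +1.2 and a true median of 30 gives +3.7. If q is instead taken relative to documented progression, the f = 1 row becomes about +0.8, +1.7 and +2.9. At q = 0.3 and f = 1, changing the assumed 12 months to 3, 6 or 24 gives about +8.8, +7.2 or +1.7.

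**The case against.** The strongest reply is that the intended rule is plain. Section 5.1 lists 2L start, Section 7.2 names it as a censoring date, Section 1 calls it a censoring event, and the endpoint is framed as first-line. Section 2 says italic text comes from the protocol, and the Appendix 2 row is italic, so it is probably protocol wording left unamended. A reader who takes time from Section 5.1 and asks whether an event has occurred by then would censor Patient A at month 10. On this view the matter is an incomplete edit.

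Most of that is fair, and the remedy below keeps the evident intent. It does not remove the conflict. The italic convention gives the row no lower standing, the row sits in the list of variables to be derived, and nothing sets precedence. Section 1 records that this same rule was already left out once and noticed only when a manuscript draft was reviewed.

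The illustration can also be criticised. The unrecorded-failure results depend heavily on how q is defined and on the assumed 12 months, and death is not modelled separately. That stands: the numbers show that either direction is possible and do not estimate the effect.

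Lastly, the study is descriptive and single-arm with no hypotheses, so omitting sensitivity analyses contradicts nothing. That also stands. The supportive runs below are optional.

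**Conclusion.** The concern holds. Three current texts give the same patient different rwPFS times or statuses, and Section 7.2 as worded makes censoring depend on later outcome. Neither conclusion needs an assumption.

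The size and direction of the effect on reported rwPFS cannot be determined from the SAP. The Section 5.1 and Appendix 2 curves agree only if switching is unrelated to progression risk and the hazard is unchanged after the switch. In the main illustration the difference in medians ran from -1.4 to +4.6 months, and it went higher when the time from switch to documented event was shortened. Those figures rest wholly on the assumed median, switch rate and post-switch behaviour. This should be fixed; the error is easy to correct and would give a wrong result if the wrong text were programmed.

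**What to change.** Put one rule in Section 5.1, Section 7.2 and Appendix 2, for example: *Event = first clinician-assessed progression or death on or before 2L start and by study end; patients with no such event are censored at the earliest of 2L start, last contact or study end.*

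Two details need care.
- Do not require death to fall on or before last contact. Section 2.1 takes deaths from outside sources such as the Social Security Death Index and obituaries, and Appendix 2 defines last contact only for living patients.
- State whether the progression date or the clinician confirmation date is compared with 2L start. Appendix 2 holds both, and a progression confirmed just after a switch would be classified differently.

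Report how many patients are censored at 2L start, split by the recorded therapy start reason. As optional support, add two Kaplan-Meier runs: one counting 2L start as an event (conservative, since some switches are not failures) and one ignoring 2L start (the present Appendix 2 rule).

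The cost is wording in three places, one count and, if wanted, two runs on existing data. The reported rwPFS range may look less favourable.

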 - c. Real-world time to treatment discontinuation (rwTTD) from the start of the first-line therapy at time points 3, 6, 12, 18, 24, 30, and 36 months.
 - d. Real-world time to next treatment (rwTTNT) from the start of the first-line therapy at time points 3, 6, 12, 18, 24, 30, and 36 months.
 - e. Real-world time to chemotherapy (rwTTC) from the start of the first-line therapy at time points 3, 6, 12, 18, 24, 30, and 36 months.
 - f. Real-world time to dose adjustment (rwTTDA) from the start of the first-line therapy at time points 3, 6, 12, 18, 24, 30, and 36 months.

5.1 Definitions/Derivations for Demographic, Clinical characteristics, treatment pattern and Efficacy/Effectiveness Endpoint(s)

- Age at initial diagnosis, A/MBC diagnosis, at start of palbociclib treatment and death. - They will be categorized into age categories: <50, 50-64, 65 –74, ≥75 years.
- Time to metastasis- It is defined as months between initial and metastasis diagnoses. It will be categorized into ≤12 months, 13-24 months, 25-36 months,>36 months and de novo metastatic.
- Disease Free Interval (DFI)- It is defined as months from the end of adjuvant therapy to the date of disease recurrence. It will be categorized into ≤12 months, 13-24 months, 25-36 months,>36 months and Unknown.
- Line of therapy- The line number (1; 2; 3; etc.) in the A/MBC setting will be assigned based on Syapse line of therapy algorithm.
- Regimen medication(s)- Systemic therapies included in line regimen defined by Syapse line of therapy algorithm.
- Time to first dose change- It is defined as days from palbo dose 1 start date to palbo dose 2 start date, if applicable.
- Number of dose changes- Number of dose reduction(s) and number of dose increases over the calendar time (quarter since February 2015) and over treatment cycle since palbo dose 1 start date.
- Real-world Overall Survival (rwOS)- It is defined as length of time from the start of palbociclib + AI treatment to the earliest of the following: date of death, date of last contact, or the end of study period
- Real-world progression free survival (rwPFS)- It is defined as length of time from the start of palbociclib + AI treatment to the earliest of the following: clinician-assessed progression event (sources include medical oncology consult/note, radiation oncology note and discharge summary), date of death, date of initiation

PFIZER CONFIDENTIAL

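### rwPFS is censored at second-line start whatever the reason for the switch; recorded reasons of Progression go unused, so upward bias is possible and no planned analysis would show it

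*SAP*

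**What the plan says.** Section 5.1 ends rwPFS time at the earliest of "clinician-assessed progression event (sources include medical oncology consult/note, radiation oncology note and discharge summary), date of death, date of initiation" "of the 2nd line for patients with >1 line of therapy, date of last contact, or end of study period". It does not say which of these are events. Section 1 settles second-line start: "Included the initiation of 2nd line of therapy as a censoring event in the definition of progression-free survival". Section 7.2 states the rule for the Kaplan-Meier analysis: "Patients without a clinician-assessed progression event or death will be censored at the earliest of the following events: date of initiation" of the second line, last contact, or end of study. Neither section refers to why therapy changed.

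Appendix 2 (Section 9.2) gives a third rwPFS definition that does not list second-line start. It also sets the standard for a progression: "Progression identified from tissue/pathology or imaging/radiology and confirmed by clinician (in 2 separate data points), from MA guidance", followed by a list of acceptable note types.

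Appendix 2 separately captures, for each therapy, a start reason ("Recurrence; Progression; Other reason not related to worsening disease") and a stop reason ("Categories including: Progression; Toxicity; End of planned therapy; Insurance changes; Treatment ongoing; Other"), each with a source date. It allows that date to be linked to the clinician confirmation of recurrence or progression, but does not require it. No rwPFS rule uses these fields.

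**The concern.** Kaplan-Meier estimation assumes that a censored patient has the same later risk as patients still under observation. A patient whose first-line therapy was changed because of progression does not: the event has already happened. If that progression has no record meeting the rwPFS standard, the plan treats the patient as event-free up to the switch and then removes the patient from the risk set. The same patient could be counted under Progression as discontinuation reason in Table 15.4.5 and as censored in the rwPFS table.

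rwPFS is one of the effectiveness outcomes under the primary objectives, so its median and seven landmark estimates matter to the report. Section 7.2 plans one Kaplan-Meier analysis per endpoint, repeated for the 125 mg starting dose, and the Section 7.2.2 table adds metastasis status for rwPFS. None of these varies the censoring rule. The table shell to be reused for rwPFS gives only a total number censored.

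**Working it through.** The SAP states no rwPFS median, event count or share of undocumented progressions, so there is no plan figure to reproduce. The check has two parts: what each definition does with the patient at issue, and how large the effect could be under stated assumptions.

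**The three definitions.** Take a patient who progresses on first line without a qualifying record and then starts second line.

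- Section 5.1: the clock stops at second-line start and the patient is censored there.
- Section 7.2, read literally: only patients with no progression or death at all are censored at second-line start. A documented progression or death on second line could therefore still count, at its later date. With no later event, the patient is censored at second-line start.
- Appendix 2: second-line start is not listed, so follow-up runs on to a later progression, death, last contact or end of study.

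In all three, the first-line progression is either not counted or counted late. The direction is upward in each; the size differs.

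**Size under the Section 5.1 reading.** Assumptions, none of them from the SAP:

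- time to first event exponential, true median 20 months (15 and 25 also run);
- 15% of first events are deaths, which cannot be lost in this way;
- a share f of progressions lacks a qualifying record;
- second line starts 1 month after such a progression;
- follow-up uniform over 6 to 60 months. The range matches the SAP: 31 July 2019 to 01 February 2020 is 6.1 months, and 03 February 2015 to 01 February 2020 is 59.9 months.

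Closed form, ignoring the 1-month lag: the true hazard is h = ln 2 / 20. Progressions are 0.85 of first events, so 0.85f of events become censorings and the observed event hazard is (1 − 0.85f)h. Hence

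- apparent median = 20 / (1 − 0.85f);
- apparent 24-month rwPFS = 0.5^[(24/20)(1 − 0.85f)].

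For f = 10%: median = 20 / 0.915 = 21.9 months; 24-month rwPFS = 0.5^1.098 = 46.7%.

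Simulation of 400,000 patients, with the lag and with no switching for other reasons:

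| f | Closed-form median | Simulated median, SAP rule | Simulated 24-month rwPFS, SAP rule | Simulated median, switches for progression counted as events |
|---|---|---|---|---|
| 0 | 20.0 | 20.0 | 43.6% | 20.0 |
| 5% | 20.9 | 20.9 | 45.2% | 20.1 |
| 10% | 21.9 | 21.9 | 46.9% | 20.1 |
| 20% | 24.1 | 24.3 | 50.4% | 20.2 |

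The last column places the event at second-line start, which explains the small remaining excess over 20.

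For other true medians, the SAP rule gives 15.6, 16.4 and 18.1 months (true 15) and 26.1, 27.4 and 30.3 months (true 25) for f = 5%, 10% and 20%.

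**Switches for other reasons.** With independent switching for non-progression reasons at 0.5% per month, f = 0 still gives a median of 20.0 under the SAP rule, so censoring such switches does no harm when they are independent of risk. Counting every second-line start as an event would instead give about 17.6 months for a true 20. A useful sensitivity analysis therefore has to depend on the recorded reason.

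**The case against.** The strongest reply is that the affected patients may not exist. Appendix 2 allows the reason's source date to be tied to the clinician confirmation of progression, and it also captures whether a progression was linked to therapy. A stop reason of Progression may therefore rest on the very record that makes an rwPFS event. The accepted sources are broad: they include progress and nursing notes, scanned and outside records, and an Other category, and the progression test source may be Unknown. Sections 5.1 and 7.2 speak only of a clinician-assessed event. All of this stands. It means the share f cannot be taken from the SAP and may be small or zero. It does not close the gap, because linkage is optional and nothing says how an unlinked case, or one with an Unknown test source, is handled.

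Second, censoring at second-line start is a deliberate choice and is defensible for switches due to toxicity, insurance or end of planned therapy, in a single-arm descriptive study without hypotheses. This also stands, and it is why the main rule need not change.

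Third, rwTTNT counts next-line start and death as events, and Tables 15.2.2.4 and 15.4.5 report progression details and discontinuation reasons. These allow a rough aggregate comparison. But rwTTNT mixes in switches for other reasons, and neither table identifies who was censored in rwPFS, so the effect cannot be isolated.

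A reader might go further and infer that rwPFS is overstated as a matter of fact, or that every such patient is censored at second-line start. The documents support neither. The first needs a share that the SAP does not give. The second follows from Section 5.1, but not from the literal wording of Section 7.2 or from Appendix 2.

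**Conclusion.** The point holds in conditional form. The plan censors second-line starts without regard to the recorded reason, holds the fields that would separate progression-driven switches from others, and neither uses them nor counts censorings by reason. To the extent that progression-driven switches lack a qualifying record, the censoring is informative and rwPFS medians and landmarks could be biased upward. With complete linkage the bias is nil.

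Under the assumptions above, the inflation of a 20-month median is about 4.5% (0.9/20), 9.5% (1.9/20) and 21.5% (4.3/20) when 5%, 10% and 20% of progressions are undocumented. These figures illustrate how sensitive the estimate is; they do not predict this study's result. They apply to the Section 5.1 reading. Under the other two readings the direction is the same, but the size was not calculated.

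**What to change.** 1. Reconcile the rwPFS definitions in Section 5.1, Section 7.2 and Appendix 2 on second-line start. In particular, state whether a progression or death after second-line start can still count.
2. Keep the stated censoring rule for the main estimate.
3. In the rwPFS Kaplan-Meier table, report the number censored at second-line start by recorded start or stop reason.
4. Add one sensitivity Kaplan-Meier analysis. In it, a first-line stop or second-line start with recorded reason Progression or Recurrence but no qualifying record counts as an event at the reason's source date, or at second-line start if that date is missing or later. Switches for other reasons stay censored.

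The cost is some table rows and one extra run on fields already abstracted. The downside is a possibly less favourable sensitivity estimate. If the count in item 3 is near zero, the sponsor has direct evidence that this rule does not affect the main result.
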